1. SPONSOR INFORMATION

The regulatory sponsor is Imperial College London.

LIST OF ABBREVIATIONS 2.

AE	adverse event
BBB	Blood-brain barrier
BI	Barthel index
CRF	case report form
CRO	contract research organization
CNS	Central nervous system
CT	computed tomography
EC	ethics committee
EDC	electronic data capture
EU	European Union
LAR	legally authorized representative
LKN	Last known normal
ICF	informed consent form
ICH	International Conference on Harmonization
IRB	Institutional Review Board
MoCA	Montreal Cognitive Assessment
MRI	magnetic resonance imaging
mRS	Modified Rankin scale
NIHSS	National Institutes of Health stroke scale
PET	Positron emission tomography
PHI	protected health information
RDC	remote data capture
SABR	Safety and Benefit-Risk
SAE	serious adverse event
SUSAR	suspected unexpected serious adverse reactions
TSPO	Translocator protein
UK	United Kingdom

3. SYNOPSIS

Tracking Number: GBR-TYS-16-11060

Protocol Title: TSPO PET as a measure of post-stroke brain inflammation:

a natural history cohort

Version Number: 2.0

Name of Study Treatment: Not applicable

Study Indication: AIS

Phase of Development: NA

Rationale for the Study: Stroke is a leading cause of mortality and serious long-term

disability. There is a substantial unmet medical need for new

therapies that can improve outcomes in acute stroke.

Experimental and pathologic data suggest that peri-infarct inflammation contributes to secondary injury after brain ischemia and that blocking inflammation could reduce the volume of brain infarction and improve clinical outcome.

In a recently completed phase 2 placebo-controlled clinical trial, the administration of natalizumab (a potent inhibitor of leukocyte transmigration through the blood –brain barrier [BBB]) in the hyperacute phase of ischemic stroke was associated with beneficial effects in measures of functional outcome, but did not affect the rate of infarct volume growth

during a 90-day assessment period. This apparent

discrepancy between the lack of effect of anti-inflammatory therapy on lesion size and a substantial beneficial effect on functional outcome in ischemic stroke patients has raised

further questions about the manifestation of

neuroinflammation, its pathophysiological role and its relation to patients' functional outcome in stroke patients.

The purpose of this imaging study is to characterize the subacute and longstanding extent of upregulation of the neuroinflammation marker TSPO on glial cells at two time points after stroke. The study will also explore the correlation of TSPO upregulation with measures of stroke

severity and post-stroke functional outcomes.

Study Objectives and Endpoints:

The objectives of this study are:

- To characterize TSPO glial expression in specific regions of interest defined on correlative brain MRI (ROIs; infarct, peri-infarct, thalamus) in the subacute (day 15+7) and chronic (day 90+/-7) phases after an ischemic stroke;
- To determine the magnitude and variability of TSPO uptake at these ROIs during the assessment period;
- To describe changes in TSPO expression between 15 and 90 days
- To explore the relationship between TSPO uptake, blood and infarct volume, and measures of Wallerian degeneration,
- To characterize post-stroke TSPO glial expression in relation to measures of stroke severity (infarct size, volume and location; NIHSS) and functional outcome (mRS,BI, depression scale, MoCA)
- To characterize post-stroke TSPO glial expression in relation to systemic inflammatory markers in blood

The endpoints that relate to these objectives are:

- PET-derived measures of TSPO radiotracer uptake in the infarct and peri-infarct areas at day 15 and day 90 after a stroke
- PET-derived measures of TSPO radiotracer uptake in ROIs distant from the infarct area (e.g. thalamus, hippocampi, amygdalae and midbrain) at day 15 and day 90 after a stroke
- Correlation of PET-derived measures with clinical and imaging measures of stroke severity (stroke volume, size and NIHSS) and functional outcome (mRS Barthel index, MoCA, depression,) at day 15 and day 90
- Correlation of infarct volume and MRI measures of white matter tract injury determined from DTI MRI with measures of thalamic TSPO uptake (timeactivity curve; measures of mean and max TSPO uptake on summed image sets from TSPO PET
- Correlation of PET derived measures with inflammatory markers in the blood (e.g. cytokines)

Study Design: This is an exploratory, prospective, natural history, imaging

cohort study.

Study Location and Number

of Sites:

The recruiting site will be Imperial College Healthcare NHS

Trust. All study scans will be performed by Imanova,

Hammersmith Hospital

Number of Planned Subjects: Between 15 and 25 subjects, with recruitment ending when

15 participants have completed all study procedures.

Study Population: Subjects aged 18-85 with a supratentorial ischemic stroke of

moderate severity as measured by NIHSS >4 and evidence

of infarction on clinical brain scan at time of stroke:

Duration of Treatment and

Follow-up:

Subjects will participate in this study for approximately 90

days. No treatment will be started as part of the trial

4. SCHEDULE OF EVENTS

Tests and Assessments	Screening visit ⁹	Day 15 (±3 days)	Day 90 (±7 days)
Eligibility confirmation ¹	X		
Sign Informed Consent Form ²	X		
Demographics and medical history	X		
Physical and neurological examination	X	X	X
Vital signs ³	X	X	X
Height (if available) and weight	X		
Urine (or serum) pregnancy test ⁴	X	X	X
Medications	X		
NIHSS		X	X
mRS		X	X
BI		X	X
Beck Depression Inventory		X	X
Hematology and blood chemistry ^{5,6}	X		
Blood sample for systemic inflammatory profile	X	X	X
Blood sample for TSPO polymorphism genotyping ⁷	X		
Confirmation of genotype eligibility criterion ⁸		X	
PET and MRI scanning		X	X
Adverse Events reporting		throughout	

- 1. All but genotype exclusion criterion, see bullet point 8
- 2. Subjects will be consented prior to screening procedures
- 3. Vital signs include temperature, blood pressure, pulse or heart rate and respiratory rate
- 4. Women with childbearing potential only
- 5. Liver function, renal function and CBC will be performed at screening. Results of tests performed as part of standard of care can be accepted.
- 6. Renal function tests will be repeated before each PET MRI assessment in subjects older than 60 years of age or with known renal impairment
- 7. SNP genotype confirmation is required to determine eligibility. Blood samples for this assessment will be collected at screening only after other eligibility criteria have been met
- 8. Verification of the TSPO SNP genotype exclusion criterion will occur prior to or at the PET MRI acquisition day but will be confirmed before subjects undergo PET-MRI imaging acquisition.

CONFIDENTIAL

The information contained herein may not be used, disclosed, or published without the written consent of the Sponsor-Investigator.

9. Up to 10 days from stroke onset

5. INTRODUCTION

5.1. Background

Stroke is a leading cause of mortality and serious long-term disability. There is a substantial unmet medical need for new therapies that can improve outcomes in acute stroke. Experimental and pathologic data suggest that peri-infarct inflammation contributes to secondary injury after brain ischemia and that blocking inflammation reduces the volume of brain infarction and improves clinical outcomes.^{1, 2} Hence, immunologic therapies have been investigated for treatment of ischemic stroke.³ Nevertheless, there is substantial uncertainty about the time course and anatomic distribution of inflammation after stroke as well as its contribution to functional outcomes.

5.2. Rationale

TSPO, previously known as the peripheral benzodiazepine receptor (PBR), is a cholesterol transport protein that is present mainly in the mitochondrial compartment where it facilitates flow of cholesterol into mitochondria during steroid synthesis. ⁴ TSPO is overexpressed by microglia and monocyte-derived cells during inflammation and has been extensively used as a measure of inflammation.

In the brain, TSPO PET radioligands provide a measure of predominantly resident (activated) microglia and infiltrating monocyte-derived macrophages and, to a lesser extent, reactive astrocytes. ⁵

Ischemic stroke is arguably one of the most robust examples of CNS inflammation following acute brain injury. As such, TSPO PET scans have been used to assess brain inflammation for over two decades. 11C-PK11195, a first generation radioligand, was used by several investigators to study the magnitude of inflammation after the occurrence of an acute ischemic stroke in humans. Table 1 below summarizes the key findings of these studies:

Table 1: Literature on 11C-PK11195 PET imaging in human ischemic stroke

Author/Date	Number of subjects studied	Key findings
Ramsay 1991	1	Uptake in infarct zone at 13d and 20d
Pappata 2000	7	All MCA stroke, imaged 2-24 months after stroke. Increased binding in ipsilateral thalamus and ipsilateral midbrain (not contralateral thalamus)
Gerhard 2000	5	Uptake at 5-33 days
Gerhard 2005	6	Early uptake in infarct zone

TSPO PET as a measure of post-stroke brain inflammation

		Late uptake in thalamus/Wallerian degeneration
Price 2006	4 stroke, 4 control	Uptake in infarct, peri-infarct and contralateral brain increases from day 0-3, further at 7-14, and further at day 25-30
Radlinska 2009	21	Uptake along pyramidal tract as defined by DTI MRI within 2 weeks of acute ischemic stroke
Thiel 2010	18+ 6 controls	Uptake at 2 weeks, persisting to 6 months Persistent uptake correlates with a worse clinical outcome

As a summary, in these earlier TSPO PET studies there was an observable increase in PET radioligand uptake in the infarct zone at early time points, which increased up to 30 days after the stroke. ^{6,7} In addition, development of an increased uptake at brain regions that are distant from the primary infarct area (i.e. thalamus and brainstem) was observable at later time points and seemed to be associated with areas of Wallerian degeneration, as demonstrated by concomitant acquisition of diffusion tensor imaging (DTI) on brain MRI. ⁸ Furthermore, the degree of microglial activation on 11C-PK11195 imaging appeared to be directly correlated with the degree of white matter fiber damage at MRI, which persisted in longitudinal TSPO PET assessments for up to six months after the index stroke. ^{5,9}

Taken together, these findings provide scientific rationale to support that TSPO PET MRI is a valuable tool to assess dynamic changes in brain inflammation that occur after an event of acute ischemic brain injury, which could provide further insight on how brain inflammation relates to the natural history of the disease. Given the small size, variability in imaging time points, and cross sectional nature of the majority of these studies, larger cohorts that measure longitudinal changes and key determinants of TSPO signal changes after stroke are needed to better understand neuroinflammation after stroke in humans.

Rationale for radioligand selection

Second-generation TSPO radiotracers have been developed to overcome some of the shortcomings of 11C-PK11195, the first-generation tracer. Specifically, the on-target to off-target binding profile has been improved.

These second-generation tracers were validated in numerous types of human CNS inflammation, including multiple sclerosis, trauma, HIV encephalopathy, and chronic neurodegenerative diseases such as Parkinson's disease and Alzheimer's disease. A second-generation tracer, PBR28, has been shown to effectively identify a sub-acute ischemic stroke in a case report ¹⁰.

Despite the advantages of second-generation TSPO ligands in terms of image quality, a polymorphism (rs6971) in the gene encoding TSPO is responsible for existence of 3 classes of TSPO binders: Low-, Medium-, and High-affinity binders.^{11, 12}

Pharmacologic TSPO blockade in human studies has demonstrated that it is feasible to adjust image quantification to harmonize data between medium affinity binders (MAB's) and high affinity binders (HAB's). Low-affinity binders, which comprise no more than 10% of the population are usually excluded from TSPO PET studies due to poor signal-to-noise ratios. Hence, low-affinity binders will also be excluded in the present study.

6. STUDY OBJECTIVES AND ENDPOINTS

6.1. Objectives and Endpoints

The objectives of this study are:

- To characterize TSPO glial expression in specific regions of interest defined on correlative brain MRI (ROIs; infarct, peri-infarct, thalamus) in the subacute (day 15+3) and chronic (day 90+7) phases after an ischemic stroke;
- To determine the magnitude and variability of TSPO uptake at these ROIs during the assessment period;
- To describe changes in TSPO expression between 15 and 90 days
- To explore the relationship between TSPO uptake, blood and infarct volume, and measures of Wallerian degeneration; and,
- To characterize post-stroke TSPO glial expression in relation to measures of stroke severity (infarct size, volume and location; NIHSS) and functional outcome (mRS, BI, MoCA, Beck depression inventory)
- To characterize post-stroke TSPO glial expression in relation to systemic inflammation in blood

Endpoints that correlate to these objectives are:

- PET-derived measures of TSPO radiotracer uptake in the infarct and peri-infarct areas at day 15 and day 90 after a stroke;
- PET-derived measures of TSPO radiotracer uptake in ROIs distinct from the infarct area (e.g., thalamus, hippocampi, amygdalae and midbrain) at day 15 and day 90 after a stroke:
- Correlation of PET-derived measures with clinical and imaging measures of stroke severity (stroke volume, size and NIHSS) and functional outcome (mRS and BI) at day 15 and day 90
- Correlation of infarct volume and MRI measures of white matter tract injury determined from DTI MRI with measures of thalamic TSPO uptake (time-activity curve; measures of mean and max TSPO uptake on summed image sets from TSPO PET.
- Correlation of PET derived measures with inflammatory markers in the blood (e.g. cytokines)

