10.1.2 Magnetic Resonance Imaging (MRI)

MRI involves the use of an intense magnetic field to quantify tissue anatomical characteristics. In this study MRI will be used to define the volume of the stroke affected areas, and physiological characteristics of the brain tissue relevant to stroke physiology. In addition, a Gadolinium conjugated contrast agent will be used to assess the regional integrity (i.e. permeability) of the blood-brain-barrier. Each MRI scanning session will be up to 90 min in duration and will include the administration of a Gadolinium-conjugated contrast agent.

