12. STATISTICAL CONSIDERATIONS

12.1. Sample Size Justification

This is a natural disease progression study. Quantitative data on the uptake in and around infarcts and changes over time are not available to base a power calculation on. Therefore, sample size has been determined pragmatically, based on feasibility. The main purpose is to pilot characterization of the magnitude and variability of the change in a normalized measure of the TSPO radioligand uptake in the target regions between baseline (14 days) and 90 days post infarction in untreated patients. We chose to use a pseudo-reference region quantification as it avoids the need for radial artery cannulation in these patients. In addition, this method has a significantly better test-retest variability than the fully quantitative methods using metabolite corrected arterial plasma input function (\sim 4-5% vs \sim 20%)...²² . While such an approach may lead to an underestimation of any changes seen, ²³ due to potential changes in signal in the pseudo-reference region, we believe it is justified in this situation where a focal change in signal is expected, and will be compensated for by reduced signal variability.

The magnitude of the signal change between days 14 and 90 is unknown but it is expected that changes above 10% will be detectable given the small test/retest variability of [11C]PBR28.

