12.4. Endpoints Analysis

PET-derived measures including SUVR in the infarct and peri-infarct area, and ROIs distant from the infarct area at Day 15 and Day 90 will be summarized by visit. Various aspects of change over time including magnitude, variability and pattern will be assessed. The relationship between PET-derived measures and stroke severity (including stroke volume, size, NIHSS) will be examined using methods including linear correlation and regression. Also, the relationship between PET-derived measures and functional outcomes , markers of systemic inflammation and relationship between measures of white matter tract injury and measures of thalamic uptake will be explored.

A detailed statistical analysis plan will be established before the beginning of the analysis.

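### The planned correlation of infarct SUVR with infarct volume has no stated handling of PET partial volume loss, which can produce a positive correlation by itself when the infarct is hotter than its surroundings

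*Combined protocol and SAP*

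**What the plan says.** Section 6.1 (and the synopsis) makes the association an endpoint: "Correlation of PET-derived measures with clinical and imaging measures of stroke severity (stroke volume, size and NIHSS", at day 15 and day 90. Section 12.4 names the measures, "PET-derived measures including SUVR in the infarct and peri-infarct area, and ROIs distant from the infarct area at Day 15 and Day 90", and says that their relation to stroke severity "will be examined using methods including linear correlation and regression". No adjustment is named.

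Both variables come from the same MRI lesion. The PET regions are "specific regions of interest defined on correlative brain MRI" (section 6.1), and under section 10.1.2 "MRI will be used to define the volume of the stroke affected areas".

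The documents give no scanner resolution, reconstruction or smoothing, partial volume correction, eroded region, peri-infarct width or minimum lesion volume. Sections 8.1 and 8.2 restrict severity by NIHSS, not by lesion size. The one quantification bias discussed, in section 12.1, is signal change in the pseudo-reference region, which is a different matter. Section 12.4 leaves further detail to a later SAP.

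**The concern.** PET has finite resolution. When a blurred image is averaged over a lesion mask drawn on MRI, part of the lesion's excess signal falls outside the mask and is replaced by signal from the neighbourhood. The lost share is larger for smaller lesions. Measured infarct SUVR is then partly a function of infarct volume, even if the underlying uptake is the same in every patient.

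Section 5.2 summarises the earlier studies as showing raised uptake in the infarct zone. If that uptake exceeds the uptake around it, the bias is positive. A positive correlation could then be read as more intense inflammation in larger strokes when it reflects the camera. A larger cohort does not help: the bias stays the same and the test becomes more likely to flag it.

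**Working it through.** The plan gives no figure for this correlation and no power calculation ("sample size has been determined pragmatically, based on feasibility"), so there is nothing to reproduce. The mechanism was tested directly.

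**Inputs from the documents.** N is 15 completers, at most 25 enrolled (synopsis). The method is linear correlation (12.4). Test-retest variability is about 4-5% (12.1).

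**Assumptions, not in the documents.** Spherical infarct; Gaussian blur; background SUVR 1.0; true infarct SUVR 1.5 (excess 0.5) unrelated to volume; infarct volume lognormal with median 15 mL and log-SD 1.2; measurement noise 4.5%; two-sided 0.05.

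**Step 1: recovery.** Radius R = (3V/4π)^(1/3), so 1 mL gives 6.2 mm and 100 mL gives 28.8 mm. With σ = FWHM/2.355, the blurred unit sphere at distance r from its centre is

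f(r) = ½[erf((R+r)/√2σ) + erf((R−r)/√2σ)] − σ/(r√2π) · [exp(−(R−r)²/2σ²) − exp(−(R+r)²/2σ²)].

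Recovery is its mean over the mask, RC = (3/R³)∫₀ᴿ f(r) r² dr.

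| FWHM | 1 mL | 5 mL | 20 mL | 100 mL |
|---|---|---|---|---|
| 4 mm | 0.68 | 0.81 | 0.88 | 0.93 |
| 6 mm | 0.54 | 0.72 | 0.82 | 0.89 |
| 7 mm | 0.47 | 0.67 | 0.79 | 0.88 |

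At 6 mm in normal surroundings, a true 1.5 reads 1 + 0.5 × 0.54 = 1.27 at 1 mL and 1 + 0.5 × 0.89 = 1.45 at 100 mL.

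**Step 2: the surroundings.** Add a 10 mm rim (assumed width). With infarct excess E and rim excess Q, the infarct mask reads approximately 1 + (E − Q) × RC + Q, because the rim's outer edge is far enough away to matter little. At 6 mm, RC is 0.624 at 2 mL and 0.908 at 150 mL:

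| Pattern | E, Q | 2 mL | 150 mL |
|---|---|---|---|
| Hot infarct, normal rim | 0.5, 0 | 1.31 | 1.45 |
| Hot infarct, warm rim | 0.5, 0.25 | 1.41 | 1.48 |
| Equally hot | 0.5, 0.5 | 1.50 | 1.50 |
| Cold core, hot rim | −0.2, 0.5 | 1.06 | 0.86 |

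The sign of the bias is the sign of E − Q.

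**Step 3: simulated studies, n=15, 6 mm, no true relation, rank correlation.** Excess CV is the between-person spread of the excess.

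| Surroundings | Share with p<0.05, excess CV 10-40% |
|---|---|
| Normal | about 39% down to 12% (median correlation 0.45 down to 0.22) |
| Rim at half the infarct excess | about 13% down to 7% |
| Rim equal to infarct | about 5% |

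With normal surroundings, over 4-7 mm and excess CV 10-60%, the share runs from about 6% to 51%.

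**Step 4: a second set of assumptions.** Here volumes are log-uniform over 2-150 mL, the CV is on SUVR itself, and the test is Pearson on log volume, at 6 mm with a normal rim and n=15. The mean r is +0.54, +0.31 and +0.16 at CV 5, 10 and 20%, with p<0.05 in 60%, 21% and 9% of cohorts. At n=25 and CV 10% the share is 37%. With volumes of 10-150 mL only, it is 7-11% (4-8 mm, n=15, CV 10%). A cold core in a hot rim gives r = −0.61 at CV 10%. With blurring removed, the share returns to 4-6%.

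**Step 5: peri-infarct region.** With a raised rim and CV 10%, r lies between −0.01 and +0.10 and p<0.05 occurs in about 4-6%. Beside a normal rim, spill from the infarct moves the reading only from 1.017 at 2 mL to 1.038 at 150 mL.

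**The case against.** The strongest objection is that the bias is conditional, and the condition may not hold. Table 1 in section 5.2 includes a study reporting rising uptake in infarct, peri-infarct and contralateral brain, and the plan treats peri-infarct uptake as an endpoint of its own. If the rim is nearly as hot as the infarct, little bias remains. This stands: a reader might infer that blurring always creates a positive correlation, and it does not.

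The assumed spread also matters. An excess CV of 10-40% on an excess of 0.5 is an SD of 0.05-0.20, or 3-13% of an SUVR of 1.5. The cohort mixes medium- and high-affinity binders and ages 18-85, so the spread may be wider. At excess CV 60% (0.30/1.5 = 20% of SUVR) the share with p<0.05 is about 9%. This stands as a limit on size.

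The study is exploratory, states no significance level, and defers detail to a later SAP. This stands too: the handling is unspecified, which does not mean that it will not be done.

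Two further readings are tempting and unsupported. The gap between 1.27 and 1.45 (about 14%) might be set against the 10% in section 12.1. That figure concerns change between two scans of the same person, not a difference between patients. A reader might also extend the result to peri-infarct SUVR. There the effect is small when the rim itself is raised, and it depends on a rim width that the documents do not give.

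**Conclusion.** The concern holds for the infarct region, as an unspecified and conditional bias. Infarct SUVR and infarct volume are linked by resolution as well as by biology, and the documents do not say how the two will be separated. If the infarct is hotter than its surroundings, blurring alone can give a positive correlation. At n=15 and 6 mm, nominal significance appears in about 12-39% of null studies with normal surroundings, about 7-13% with a rim at half the infarct excess, and about 5% with an equal rim. A cold core in a hot rim reverses the sign. Direction and size therefore cannot be interpreted without knowing the resolution, the lesion volumes and the uptake next to the infarct.

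These figures rest on a sphere-and-rim model and on assumed resolution, volumes and spread. They show what is possible; they do not predict this cohort's result. The consequence is for the interpretation of an exploratory endpoint. Regions distant from the infarct were not modelled.

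**What to change.** In section 12.4 and the later SAP:

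- Keep the uncorrected infarct SUVR-volume correlation and report beside it a sensitivity analysis with partial volume correction. The correction should use the MRI infarct and peri-infarct masks, the scanner's resolution and the measured uptake of neighbouring tissue. Recovery for an isolated lesion is not enough, because the bias depends on the difference between infarct and rim.
- State the scanner resolution and the peri-infarct width.
- Show the correlation that blurring alone would produce with the cohort's own volumes.
- Do not interpret an uncorrected correlation as more intense inflammation in larger strokes without that comparison.

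Adding volume as a covariate is no remedy, since volume is the variable under study. Nor should the relation count as real only if it survives correction: with about 15 patients and noisier corrected values, a true relation could fail through noise.

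The cost is extra image-analysis work, with no new scans or visits. The downside is the added noise in the corrected values, which is why both results should be shown.
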